9.4.3. End of Treatment: Research Samples

All patients

- Whole blood sample for ctDNA, DNA methylation profiling/future research (optional)
- Surgery site to ship FFPE tissue from the surgical resection to RNOH (coordinated by UCL CTC)

Patients on PBMC substudy (UCLH site only)

• Whole blood samples for PBMCs

9.5. Follow up

9.5.1. Follow up: Clinical Data

Follow up visits should take place, at least annually, according to routine practice, on all patients including those who did not receive treatment. The following details should be collected:

- Disease status
- Survival status
- Details on any post-operative complications (e.g. deep implant infection)
- Adverse reactions: assessed only in relation to study procedures, e.g. venepuncture, biopsy for research, when applicable

Please continue completing all follow up forms after patient has relapse/metastasis.

9.5.2. Follow up: PROs

• Patients aged 13 or over should complete the PROs including SAM, EORTC-QLQ-C30, TESS, GRC annually from registration until relapse.

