	 Assess the value of the Sarcoma Assessment Measure (SAM) for longitudinal assessment of patient quality of life and identify predictors of variance in patient reported outcomes (PROs) 			
	 Describe the routes and timescales of diagnostic pathways for patients with OS, and assess whether this has any impact on patient outcome 			
Target accrual:	A minimum of 350 patients (including those already recruited in ICONIC).			
Eligibility criteria:	Inclusion criteria			
	 New histological diagnosis of osteosarcoma or in the absence of osteoid seen on biopsy, pathology and imaging supportive of a diagnosis of osteosarcoma 			
	 Written informed consent of patient and/or parent/legal guardian or written confirmation of opinion of person with duty of care where applicable 			
	Exclusion criteria			
	Diagnosis more than four months prior to registration			
Number of sites:	At least 25 sites representing OS specialist oncology and surgical sites across the UK			
Treatment summary:	Treatment will be given as per usual standard of care.			
	No treatments are specified by this protocol.			

Patient study activities:

Clinical data collection

Clinical data will be collected on a regular basis. Data to be collected include baseline characteristics, treatment details, results of key investigations (including blood tests and scans), patient status (including performance status) and outcome.

Tissue and blood collection

- Tissue for FFPE and fresh freezing according to local policy will be collected during routine procedures at diagnosis, at surgery and at relapse if clinically indicated.
 - Optional study specific biopsies will be requested at relapse in cases where a biopsy is not clinically indicated.
- Blood samples will be collected from patients receiving chemotherapy and/or surgery at the same timepoints as tissue, with an additional sample presurgery and further optional samples.

Patient Reported Outcomes (PROs)

Sarcoma Assessment Measure (SAM) questionnaire

Patients ≥13 years of age will be requested to complete a Sarcoma Assessment Measure (SAM) questionnaire along with TESS, EORTC-QLQ-C30 and Global rating of change (GRC) at registration, annually and at relapse.

Prediagnostic data collection

- Patients ≥13 years will be requested to complete a questionnaire at registration detailing symptoms and routes to diagnosis.

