9.6. Relapse (local recurrence or metastases)

9.6.1. Relapse: Clinical Data

The following data should be collected on confirmation of relapse (local recurrence or metastases) and at every subsequent relapse:

- Site(s) of relapse (local, distant etc.)
- Treatment received (surgery for local recurrence or metastases, systemic therapy, radiotherapy etc.)
- Adverse reactions: assessed only in relation to study procedures, e.g. venepuncture, biopsy for research.

Please continue completing all follow up forms after patient has relapse/metastasis.

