PRO analyses will be largely descriptive, so no power calculation is provided. However, as with all descriptive analyses, the more data we acquire the more likely it is to describe our patient population accurately.

Re	search questions	Pla	anned analysis
1.	Describe longitudinal changes in PRO and functional wellbeing beyond a year after diagnosis	•	Quality of life questionnaires will be analysed using mixed modelling and results reported by each domain with summary statistics. Models will work with the date of assessment, rather than
2.	Determine the emotional impact of being diagnosed and living with OS		predefined timepoint, to account for varying treatment pathways.
3.	Examine the relationship between prediagnostic intervals and PROs	•	Mixed modelling will be used to assess whether prediagnostic interval is associated with quality of life post diagnosis.
4.	Identify factors predicting lower quality of life, physical function and impaired emotional wellbeing.	•	Mixed modelling will be used to assess which factors have an impact on quality of life post diagnosis.

17.3. Transition between Stage 1 and Stage 2

At the end of Stage 1, the analyses described in section 17.2.1 were performed. The analyses proposed for Stage 2 were reviewed during the transition and altered as above based on the findings.

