APPENDIX 2: QUICK REFERENCE GUIDE TO PATIENT VISITS

Schedule: Patients Receiving Surgery Alone +/- Adjuvant Chemotherapy	Preregistration	Within 28 days after registration	Surgery	End of Treatment (After Adj Chemo, NOT mifamurtide)	Follow up	Relapse (local recurrence or metastases)	For registration For data collection For PROs For Tissue/Blood collection
Histological confirmation of osteosarcoma. Age & sex	Х						A. WHO PS for patients ≥16 years. Lansky PS for patients <16 years.
Informed consent	Х						B. Haematology: Hb, ANC, lymphocytes, platelets. Biochemistry: CRP, albumin,
Relevant Medical History		Х					ALP, LDH, Creatinine.
Cancer signs & symptoms		Х					C. If surgery is performed prior to registration.
Smoking status, Height and Weight		Х					D. In accordance with Osteosarcoma TMN version 8, 15/01/18.
WHO/Lansky PS ^A		Х	Х				E. For trial specific procedures only e.g. phlebotomy, relapse biopsy if not SOC.
Haematology & Biochemistry ^B		Х	Х	Х			F. SAM Booklet: Sarcoma Assessment Measure (SAM), EORTC QLQ-C30,
Data collected on primary tumour diagnostic imaging		Х					Toronto Extremity Salvage Score (TESS) and Global rating of change scale
Data collected on primary tumour biopsy/surgery ^c		Х					
Data collected on diagnostic imaging		Х					(GRCS) for patients 13 years and over only.
Osteosarcoma TNM staging ^D		Х					G. Annually from registration.
Data collected on treatment plan		Х					H. Complete within 3 months of registration (by parent/guardian if patient
Adverse Reactions (in relation to study procedures ONLY) ^E		X		X	Χ	X	<13).
SAM PRO Booklet (Patients ≥13 only) ^F		Х		Х	ΧG		I. To be taken at baseline, but can be taken later if this is not possible.
Diagnostic pathway questionnaires ^H		Х					J. Collect pre surgery.
Whole blood sample for germline DNA ^I		Х					K. Collected at clinic visit during follow up no more than 6 monthly.
Whole blood sample for ctDNA (optional for all patients)		ΧJ		Х	XK	X	L. Diagnostic Archival tissue - collection coordinated by UCL CTC.
Ship FFPE tumour tissue		Χ ^L	XM			Χ ^N	M. From routine surgery taking place after registration - collection coordinated
Collect frozen tumour tissue		Xo	Xo			Xo	by UCL CTC.
Collect information on frozen tumour tissue		Х	Х	Х		Х	N. If possible, collected from second sample at relapse if standard of care (SOC),
Disease status		Х	Х	Х	Χ		OR after Trial specific consent ONLY If not SOC.
Pre-operative imaging			Х				O. Relapse/Mets Frozen tissue sample will be SOC or optional for ICONIC

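### PRO timing at and after relapse contradicts itself across the protocol; if section 9.5.2 is followed, quality of life after relapse is never observed

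*Protocol*

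**What the plan says.** The protocol sets the timing of the PRO booklet (SAM, EORTC QLQ-C30, TESS and GRC, for patients aged 13 or over) in several places.

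- **Section 1.1**, patient study activities: "Global rating of change (GRC) at registration, annually and at relapse". End of treatment is not listed.
- **Section 9.4.2** requires the booklet at end of treatment.
- **Section 9.5.2**: "Patients aged 13 or over should complete the PROs including SAM, EORTC-QLQ-C30, TESS, GRC annually from registration until relapse".
- **Section 9.6.1** introduces its list with "The following data should be collected on confirmation of relapse (local recurrence or metastases) and at every subsequent relapse". The list covers site of relapse, treatment and adverse reactions; 9.6.2 covers research samples. Section 9.6 has no PRO subsection, although 9.2, 9.4 and 9.5 each have one.
- **Appendix 2**: in both schedules the SAM row is marked at baseline, end of treatment and follow-up, and is blank under relapse. The follow-up mark carries footnote G, which reads in the first schedule "G. Annually from registration".
- **Section 9.5.1**, repeated in 9.6.1: "Please continue completing all follow up forms after patient has relapse/metastasis".

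On use of the data, section 17.2.2.3 plans mixed models by date of assessment. Its first question is "Describe longitudinal changes in PRO and functional wellbeing beyond a year after diagnosis". None of its four questions is limited to time before relapse. Section 2.4 wants SAM validated as a longitudinal measure of change tied to health status.

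**The concern.** The summary promises a PRO at relapse that nothing in the operational sections tells a site to collect. The one follow-up rule written specifically for PROs ends them at that event. Clinical follow-up continues, so the contacts exist but the booklet may not be given.

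Three things are at stake. First, the questions in 17.2.2.3 concern living with osteosarcoma in the cohort as a whole. If scores end at relapse, a mixed model either describes time before relapse or extrapolates from it. Second, relapse is a major change in health status and so a natural test of whether SAM responds to change. That test is lost. Third, factors that lower quality of life by way of relapse will show only the part of their effect that appears beforehand.

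This cannot be left to the analysis plan, because it is a data-collection rule. No model can estimate a post-relapse level from the study's own data if no score was taken after relapse.

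**Working it through.** The protocol states no figure that depends on this point, and section 17.2.2.3 gives no power calculation for PROs. The check is therefore a comparison of the rules, followed by an illustration on assumed inputs.

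**Step 1. The rules side by side.**

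| Place | Booklet at relapse | Annual booklet after relapse |
|---|---|---|
| 1.1 | Yes | Annual, no stop stated |
| 9.5.2 | Not provided for | Stops at relapse |
| 9.6.1 and 9.6.2 | No item | Silent on PROs; follow-up forms continue |
| 9.5.1 | Silent | Follow-up forms continue |
| Appendix 2, first schedule | No mark | Marked at follow-up; footnote G sets no stop |
| Appendix 2, second schedule | No mark | Marked at follow-up; footnote G not legible in the text available |

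The blank under relapse is not a column lost in the layout. Aligned to their headings, the SAM rows have 6 and 8 cells, matching the 6 and 8 visit columns. The adverse-reaction row in the same schedules does carry a mark under relapse.

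There are two separate conflicts. On a booklet **at** relapse, 1.1 stands against 9.5.2, 9.6 and both schedules. On annual booklets **after** relapse, 9.5.2 stands alone against 1.1 and footnote G, with the general instruction on forms also pointing to continuation.

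**Step 2. What 9.5.2 would remove.** Planned median follow-up is about 56 months (1.1 and 17.2.2.1). Since 56 / 12 = 4.67, a patient followed for that long has four annual booklets due, at 12, 24, 36 and 48 months. Under 9.5.2, such a patient who relapses between the first and second of these supplies one of the four and no relapse booklet. The earlier scores remain in the data.

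**Step 3. Size, on assumed inputs only.** Let p be the share of living patients who are post-relapse at an assessment, d the loss in mean score after relapse on a 0-100 scale, and m the mean before relapse. Then:

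- mean of all living patients = (1 - p) x m + p x (m - d) = m - p x d
- mean of observed patients if no post-relapse score is taken = m
- overstatement = p x d

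The protocol gives neither p nor d. Its five-year survival of about 42% (section 2) is not p. Taking p from 10% to 40% and d from 0 to 20 points:

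| p | d = 0 | d = 5 | d = 10 | d = 15 | d = 20 |
|---|---|---|---|---|---|
| 10% | 0 | 0.5 | 1.0 | 1.5 | 2.0 |
| 20% | 0 | 1.0 | 2.0 | 3.0 | 4.0 |
| 30% | 0 | 1.5 | 3.0 | 4.5 | 6.0 |
| 40% | 0 | 2.0 | 4.0 | 6.0 | 8.0 |

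The formula assumes that every site applies 9.5.2 and that the mixed model recovers none of the decline from earlier scores. To the extent that either fails, the overstatement is smaller.

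**The case against.** The strongest reply is that the schedules do not stop PROs at relapse. They omit a mark at the relapse visit, but the follow-up mark stands, footnote G in the first schedule has no end point, and sites are told twice to go on with follow-up forms. A site working from Appendix 2 could well continue the annual booklet. This is right, and it rules out saying that no post-relapse PRO will be taken. It does not resolve the matter. Section 9.5.2 is the only PRO-specific follow-up rule that addresses relapse. The Appendix 2 footnotes on continuing after relapse speak of follow-up eCRFs, which suggests forms completed by site staff rather than the patient's booklet. If sites read the rules differently, collection after relapse will vary by site.

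A reader might also infer that the results will describe only relapse-free patients. They will not. Patients who later relapse contribute all their earlier scores, and patients with metastases at diagnosis are eligible. What may be missing is time after relapse.

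A reader might go further and take the results to be too favourable by a known amount, such as the 2 to 8 points that follow from p of 20-40% and d of 10-20 points. The documents support neither input, and the direction itself depends on scores falling after relapse. That is plausible but not stated.

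Finally, the PRO analyses are described as largely descriptive, model details may properly sit in a statistical analysis plan, and stopping questionnaires at relapse to spare patients would be a legitimate choice. All of this is fair, but the protocol does not state such a choice consistently: section 1.1 says the opposite.

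**Conclusion.** The contradiction is established from the text: sections 1.1, 9.5.1, 9.5.2, 9.6 and Appendix 2 do not give one rule for PROs at and after relapse. The rest is conditional. If 9.5.2 is followed, only time before relapse is observed. Whole-cohort quality of life beyond a year is then likely to be optimistic, provided scores fall after relapse, and SAM goes untested at a major change in health status. If sites differ in their reading, post-relapse scores will be collected unevenly. The size of any bias is unknown; the 0 to 8 points in the table show its range on assumed inputs and are not an estimate. The point should be acted on because it changes what the study can conclude, and scores not taken cannot be recovered later.

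**What to change.** Reconcile the protocol to one rule in line with section 1.1:

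- add a PRO item to section 9.6 and a relapse mark to the SAM row in both Appendix 2 schedules;
- remove the stop at relapse from 9.5.2, so that annual PROs continue at existing follow-up contacts while the patient is willing, and make footnote G say the same in both schedules;
- add end of treatment (9.4.2) to the list in 1.1.

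Continuing the annual booklet goes slightly beyond the letter of 1.1, which does not spell out what happens after relapse. If the sponsor prefers to stop at relapse, all of these places should say so, and the questions in 17.2.2.3 should be limited to time before relapse.

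In reporting, give quality of life for all patients alive and, separately, for time before relapse. Do not adjust the predictor models for relapse as a covariate: relapse lies on the path from some predictors to poor quality of life, and adjustment would remove that part of their effect.

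The cost is a short amendment, one booklet at relapse and continued annual ones. Section 9.2.2 already allows completion by phone or post at baseline, and the same could apply here. The downside is some burden for relapsed patients, who may decline. Booklets missed before the amendment cannot be recovered, and the study ends two years after the last patient is recruited, so the change is worth most if made early.

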9.5.3. Follow up: Research Samples

All patients

• Whole blood sample for ctDNA, DNA methylation profiling/future research collected at clinic visit during follow up no more than 6 monthly (optional).

9.6. Relapse (local recurrence or metastases)

9.6.1. Relapse: Clinical Data

The following data should be collected on confirmation of relapse (local recurrence or metastases) and at every subsequent relapse:

- Site(s) of relapse (local, distant etc.)
- Treatment received (surgery for local recurrence or metastases, systemic therapy, radiotherapy etc.)
- Adverse reactions: assessed only in relation to study procedures, e.g. venepuncture, biopsy for research.

Please continue completing all follow up forms after patient has relapse/metastasis.

9.6.2. Relapse: Research Samples

All patients

- Whole blood sample for ctDNA, DNA methylation profiling/future research (optional)
- If the baseline optional ctDNA sample was missed for any reason, please continue with the on treatment, end of treatment and follow up samples
- Tumour tissue collected as part of standard of care, or for research (optional) (FFPE and fresh/frozen
 according to local policy, if possible, and stored locally at surgical site: collection coordinated by UCL
 CTC)

Patients receiving neoadjuvant chemotherapy

• Blood samples for CTCs (only if the baseline and pre surgery samples have been collected).

Patients on PBMC substudy (UCLH site only)

Whole blood samples for PBMCs

10. EXPLORATORY BIOLOGICAL STUDIES

The following sections provide an overview of sample collection. For details of sample collection, processing and shipping, refer to the **ICONIC Laboratory Manual**.

Below are two tables outlining biological sample collection for patients receiving either neoadjuvant chemotherapy, or surgery with or without adjuvant chemotherapy. The following sections give further details on processing, collection and storage.

SCHEDULE: PATIENTS RECEIVING SURGERY ALONE +/- ADJUVANT CHEMOTHERAPY	Within 28 days after registration	Surgery	End of Treatment	Follow up	Relapse (local recurrence or metastases)
Whole blood sample for germline DNA	X				
Whole blood sample for ctDNA (optional for all patients)	X		X	Χ¹	Х
FFPE tumour tissue	Х	Х			X ²
Provide information on frozen tumour tissue ³	Х	х	Х		X ²
Frozen tissue samples sent on request	X	Х			X

- 1. To be collected at clinic visit during follow up no more than 6 monthly.
- 2. Collect if patient consents to this optional biopsy (if not already collected as part of SOC)
- 3. Where sample stored, reason sample not taken if applicable

	S.	During Tre	eatment			nce
SCHEDULE: PATIENTS RECEIVING NEOADJUVANT CHEMOTHERAPY	Baseline: within 28 days after registration	End of Neoadjuvant chemotherapy	Surgery	End of Treatment	Follow up	Relapse (local recurrence or metastases)
Whole blood sample for germline DNA	Х					
Whole blood sample for CTCs	х	х	(X) ¹			Х
Whole blood sample for ctDNA (optional for all patients)	х	х	(X) ¹	Х	X ²	Х
PBMCs (UCLH only)	х	Х	(X) ¹	Х		Х
FFPE tumour tissue	х		Х			X ³
Provide information on frozen tumour tissue ⁴	х		х	Х		X ³
Frozen tissue samples sent on request	х		Х			х

- 1. Can collect before primary resection surgery if not taken at end of neoadjuvant treatment
- 2. To be collected at clinic visit during follow up no more than 6 monthly.
- 3. Collect if patient consents to this optional biopsy (if not already collected as part of SOC).
- 4. Where sample stored, reason sample not taken if applicable

10.1. FFPE tumour tissue samples

FFPE samples should be obtained for all patients and shipped to the Royal National Orthopaedic Hospital (RNOH). These will be used to optimise processes to enable DNA/RNA extraction from samples to perform molecular targeted sequencing and copy number analysis (CNA), and to validate findings from reported and ongoing WGS studies.

The collection of samples will be coordinated centrally by UCL CTC.

10.1.1. FFPE Collection time points

The following FFPE samples will be collected:

- Archival FFPE tissue blocks from previous biopsy or surgery
- FFPE tissue blocks from routine surgery taking place after registration
- FFPE collected at relapse/mets as part of standard of care, or for research (optional) (see section 10.3 below).

10.1.2. FFPE Processing

All samples should be fixed and embedded according to local practice.

For routine samples, sites should obtain at least one and ideally two FFPE tumour tissue blocks from a previous biopsy or surgery.

Review the pathology report and select blocks as follows:

- Biopsy cores: Choose cores that have the highest tumour tissue content.
- Surgical resection tissue: Choose blocks containing the most tumour tissue.

10.1.3. FFPE Shipping

Archival samples should be shipped on request from UCL CTC.

10.1.4. FFPE Return

All FFPE samples will be stored at RNOH. During the Study sites may request return of routine samples if required for clinical purposes but would be requested to return the samples to RNOH after this.

At the end of the Study all routine FFPE samples will be returned to site.

Samples taken for research (i.e. those not clinically indicated) will not be returned to sites.

10.2. Fresh/Frozen tumour specimens

Information will be captured about routine collection of frozen tumour specimens, at baseline, surgical resection of primary tumour or metastases and on relapse/local recurrence.

- Fresh/frozen tumour specimens should be shipped on request from UCL CTC.
- At the end of the Study all routine fresh/frozen tumour specimens will be returned to site.

10.3. New biopsy samples (Fresh/Frozen and FFPE) at relapse or metastases

A new biopsy, FFPE and fresh/frozen according to local policy if possible, should be obtained at relapse/ resection of local recurrence or metastases for the study if not done as part of standard of care. This is optional for patients.

The collection of samples will be coordinated centrally by UCL CTC.

For new biopsies for research, two cores should be obtained. One core should be fresh frozen in liquid nitrogen according to local policy and one core should be formalin fixed paraffin embedded.

If it is not possible to obtain two cores, then one is acceptable and should be fresh/frozen according to local policy.

• The fresh/frozen sample should be stored at site at -80°C until requested for analysis.

10.4. Whole Blood samples for Circulating Tumour Cells

Blood samples will be collected for analysis of circulating tumour cells (CTCs) in patients receiving neoadjuvant chemotherapy.

Samples sent to Newcastle University will be used for ongoing validation of the MT1-MMP method of CTC isolation through the use of flow cytometry and subsequent genetic characterisation.

Samples sent to the University of Sheffield will be used to optimise a new method for isolating CTCs. The procedure uses the ParsortixTM System to enrich for CTCs, which are then isolated and captured using the DEPArrayTM System²².

The protocols are ready for clinical validation and a pilot study funded by Sarcoma UK to capture CTCs from patients with soft tissue sarcoma has begun recruiting. Blood samples from patients in ICONIC will enable this methodology to be validated in OS.

